### 6.3 Contract and logistics

A contract for this Surveillance must be concluded in writing with the head of each site. Contract templates of surveillance site shall be used if available.

[1] The Medical Representative (hereinafter referred to as "MR") shall provide Xeljanz Proper-use Information to doctors, pharmacists, and other relevant site staff who will handle/use Xeljanz.

[Safety information kit]

Product Summary, Proper Use Guide, explanation of "Precautions" for new pharmaceuticals, literature for use by patients, package inserts, etc.

[2] Sponsor will explain the proper use of Xeljanz to each investigator taking part in this Surveillance; after which, the investigator will sign or name/seal the "Confirmation of Cooperation to Surveillance", and submit it to the MR (this document is also required when the investigator is relocated to another site).

[Confirmation of Cooperation to Surveillance]

- Cooperation to diagnosis and treatment of serious infection, tuberculosis and malignant tumor
- Requirements for sites and doctors
- Other relevant items requiring confirmation
- Signature or name/seal of the investigator taking part in this Surveillance

[3] Upon receiving "Confirmation of Cooperation to Surveillance," a contract for this Surveillance will be concluded between the site and Sponsor.

[4] The sample size ratio between the Xeljanz group and the control group to be specified in the contract will be in principle 2 to 1. However, depending on the conditions at the medical facility, the case ratio may be adjusted between 2:1 and 1:1.

[5] Sponsor, upon confirming the conclusion of contract for this Surveillance, shall set up logistics necessary to deliver Xeljanz to the site.

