## **2.2. Study Objectives**

*This survey will be performed in patients administered Xeljanz Tablets (hereinafter referred to as Xeljanz) to obtain information on the following under the actual use conditions after marketing:*

- 1) *Development of adverse drug reactions, factors that may affect safety, and efficacy*
- 2) *Safety (malignant tumors and serious infections in particular) and efficacy in long-term use*

*The development of malignant tumors and serious infections will be compared with the control group.*

Since it has been suggested in Japanese clinical trials that Xeljanz may promote the manifestation of malignant tumors, the development of malignant tumors in the Xeljanz group will be compared with that in the control group by 3-year observation. The development of serious infections in the Xeljanz group will be compared with that in the control group by 1-year observation.

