#### **4. HYPOTHESES AND DECISION RULES**

Since this survey is not a confirmatory study, statistical tests will be exploratory. Unless otherwise specified, tests will be 2-sided and the significance level will be 5%. A 2-sided confidence interval will be used for interval estimation, and the confidence coefficient will be 95%.

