#### 8.1.5. Analysis of Incidence Rate and Incidence Proportion of Specified Events

Incidence rate and incidence proportion will be calculated for specified events including initial malignancy, initial serious infection, and death, according to the following formulae.

- **Duration of exposure [patient-year]**

Total of time to each event and time to censoring in each group [day]/365.25

- **Incidence rate amount and the 95% confidence interval**

$$\text{Incidence rate amount [patient/100 patient - years]} = 100 \times \frac{a}{PT}$$

95% confidence interval for incidence per exposure amount [patient/100 patient - years].

$$= \begin{cases} \left[ 100 \times \frac{x^2(0.025, 2a)/2}{PT}, 100 \times \frac{x^2(0.975, 2(a+1))/2}{PT} \right] & (a \neq 0) \\ \left[ 0.00, 100 \times \frac{x^2(0.95, 2))/2}{PT} \right] & (a = 0) \end{cases}$$

a: Number of patients with the event [patient]

PT: Duration of exposure [patient-year]

$x^2(p, d)$ : the lower p quantile for the chi - square distribution with d degrees of freedom

- **Incidence proportion and the 95% confidence interval**

$$\text{Incidence proportion [%]} = 100 \times \frac{a}{N}$$

95% confidence interval for incidence proportion [%]

$$= \left[ 100 \times \left( 1 + \frac{N - a + 1}{aF(0.025, 2a, 2(N - a + 1))} \right)^{-1} \cdot 100 \times \left( 1 + \frac{N - a}{(a + 1)F(0.975, 2(a + 1), 2(N - a))} \right)^{-1} \right]$$

N: Number of patients included in the analysis [patient]

$F(p, m, n)$ : the lower  $p$  quantile for the F distribution with  $m$  and  $n$  degrees of freedom.

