### 8.1.6. Group Comparison of Incidence Rate and Incidence Proportion of Specified Events

Specified events including initial malignancy, initial severe infection, and death will be compared between groups in terms of the following quantities:

- **Incidence ratio between the treatment groups and the 95% confidence interval**

$$\text{Incidence ratio} = \frac{a/\text{PT}_1}{b/\text{PT}_0}$$

95% confidence interval for incidence ratio

$$= \exp \left[ \left\{ \ln \left( \frac{a/\text{PT}_1}{b/\text{PT}_0} \right) \pm 97.5 \text{ percentile for standard normal distribution} \times \sqrt{\frac{1}{a} + \frac{1}{b}} \right\} \right]$$

Xeljanz group a: Number of patients with the event [patient], PT1: Duration of exposure [patient-year]

Control group b: Number of patients with the event [patient], PT0: Duration of exposure [patient-year]

- **Difference in incidence rates between treatment groups and its 95% confidence interval**

Difference in incidence rates [patient/100 patient-years]

$$= 100 \times \left( \frac{a}{\text{PT}_1} - \frac{b}{\text{PT}_0} \right)$$

95% confidence interval for difference in incidence rates [patient/100 patient-years]

$$= 100 \times \left\{ \left( \frac{a}{PT_1} - \frac{b}{PT_0} \right) \pm 97.5 \text{ percentile for standard normal distribution} \right. \\ \left. \times \sqrt{\frac{a}{PT_1^2} + \frac{b}{PT_0^2}} \right\}$$

- **Ratio of incidence proportions between treatment groups and its 95% confidence interval**

$$\text{Ratio of Incidence proportions} = \frac{a/N_1}{b/N_0}$$

95% confidence interval for ratio of incidence proportions

$$= \exp \left[ \left\{ \ln \left( \frac{a/N_1}{b/N_0} \right) \pm 97.5 \text{ percentile for standard normal distribution} \right. \right. \\ \left. \left. \times \sqrt{\frac{1}{a/N_1} + \frac{1}{b/N_0}} \right\} \right]$$

Xeljanz group

$N_1$ : Number of patients included in the analysis [patient]

Control group

$N_0$ : Number of patients included in the analysis [patient]

- **Difference in incidence proportion between the treatment groups and the 95% confidence interval**

$$\text{Difference in incidence proportion [%]} = 100 \times \left( \frac{a}{N_1} - \frac{b}{N_0} \right)$$

95% confidence interval [%] for the difference in incidence proportion

$$= 100$$

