**Table 6. Definitions in the Comparison of Serious Infections**

Term	Definition
Patients without serious infections	Patients who do not correspond to the each definition of patients with serious infections
Time to serious infections during the treatment period (+28 days)	Date of the development of serious infections- date of the initiation of treatment + 1 Both treatment groups will be analyzed for the duration of treatment + 28 days (up to not longer than 1 years).
Censoring period for patients without serious infections during the treatment period (+28 days)	Date of the completion of treatment + 28- date of the initiation of treatment + 1 Both treatment groups will be analyzed for the duration of treatment + 28 days (up to not longer than 1 years).
Time to serious infection during treatment period	Date of the development of serious infection - date of the initiation of treatment + 1 The upper limit is 1 year (366)
Censoring period for patients without serious infections during treatment period	Date of the completion of treatment - date of the initiation of treatment + 1 The upper limit is 1 year (366)
Time to serious infection during overall observation period	Date of the development of serious infection - date of the initiation of treatment + 1 The upper limit is 1 year (366)
Censoring period for patients without serious infections during overall observation period	Date of completion or discontinuation of follow-up - date of the initiation of treatment + 1 The upper limit is 1 year (366)

- **Development of serious infections**

The number of serious infections in each group and the proportion of occurrence are calculated for each SOC and PT. Furthermore, it is calculated for each infection type.

- **Incidence rate of serious infections**

The number of patients with serious infections in each group, incidence rate, and the 95% confidence interval will be calculated in accordance with [Section 8.1.5](#).

In addition, the incidence ratio between treatment groups and the 95% confidence interval and the difference in incidence rate between treatment groups and the 95% confidence interval will be calculated.

The above analyses will be also conducted for serious infections excluding serious herpes zoster and for serious herpes zoster, respectively.

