For covariates concerning serious infections ([Section 6.3](#)), incidence by single factor will be calculated, and the pooled incidence ratio and the 95% confidence interval and the pooled difference in incidence rate and the 95% confidence interval will be calculated.

Incidence ratio with its 95% CI will be calculated for events of herpes zoster, opportunistic infection, and tuberculosis as well as “serious infections” .

- **Incidence proportion of serious infections**

The number of patients with serious infections in each group, the incidence proportion, and the 95% confidence interval will be calculated in accordance with [Section 8.1.5](#).

In addition, the ratio of incidence proportion and the 95% confidence interval and the difference in incidence proportion and the 95% confidence interval will be calculated.

The above analyses will be also conducted for serious infections excluding serious herpes zoster and for serious herpes zoster, respectively.

For covariates concerning serious infections ([Section 6.3](#)), the incidence proportion by single factor will be calculated, and the ratio of the pooled incidence proportion and the 95% confidence interval and the difference in the pooled incidence proportion and the 95% confidence interval will be calculated. Age will be handled as categorical data.

Incidence proportion with its 95% CI will be calculated for events of herpes zoster, opportunistic infection, and tuberculosis as well as “serious infections” .

- **Analysis of time to serious infection**

- Time to serious infection in each group will be summarized in accordance with [Section 8.1.4](#). As for the censoring period in patients without serious infection, [Table 5](#) will be followed. In addition, a graph showing the transition of the incidence rate estimated using the calculated parameters by applying the Weibull distribution together with the Kaplan-Meier plot, and a graph of the transition of the hazard function are created. **Adjusted hazard ratio for the development of serious infections**

As for time to serious infection, the adjusted hazard ratio of the Xeljanz group to the control group for the development of serious infections and the 95% confidence interval will be calculated in accordance with [Section 8.1.5](#). Covariates used for adjustment are shown in [Section 6.3](#).

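### SAP 8.1.6 has no rule for zero or few events: the rare-infection incidence ratio may be incomputable, and the rate-difference interval for serious herpes zoster excludes zero from 4 versus 0

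*SAP*

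**What the plan says.** SAP section 4 sets the interval level: "A 2-sided confidence interval will be used for interval estimation, and the confidence coefficient will be 95" per cent. Section 8.1.6 then gives the between-group formulas. For a Xeljanz and b control events in PT1 and PT0 patient-years, the incidence ratio has a log-scale normal interval with variance 1/a + 1/b. The "Difference in incidence rates between treatment groups and its 95% confidence interval" uses variance a/PT1² + b/PT0². The section also has intervals for the ratio and difference of proportions, four pooled measures and hazard ratios. None of the ratio or difference formulas has a branch for zero events or an exact alternative.

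Section 8.2.3.1.2 applies these formulas to uncommon events. After asking for the rate ratio and rate difference for serious infections, it adds: "The above analyses will be also conducted for serious infections excluding serious herpes zoster and for serious herpes zoster, respectively". It continues: "Incidence ratio with its 95% CI will be calculated for events of herpes zoster, opportunistic infection, and tuberculosis as well as" serious infections overall. So serious herpes zoster gets both ratio and difference. Herpes zoster, opportunistic infection and tuberculosis get the ratio only. The time frame is short (SAP 2.2): "The development of serious infections in the Xeljanz group will be compared with that in the control group by 1-year observation".

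Sparse counts are recognised elsewhere. Section 8.1.5 uses exact limits for single-group rates, with a separate branch for zero events. Section 8.2.3.2 suppresses estimates for events with 10 or fewer patients, but that section covers the Xeljanz group alone.

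**The concern.** A large-sample interval is safe only when both groups have a reasonable number of events. For infections such as tuberculosis or serious herpes zoster, seen over one year in a control group of 2000 to 2400 patients, a control count of zero or a handful is plausible. The plan then either asks for an interval that does not exist, leaving the substitute to be chosen after the counts are known, or produces a rate-difference interval that treats zero control events as proof of a zero control rate. Because the control group is planned to be smaller, the second error falls mainly in one direction, an apparent excess for Xeljanz. Infections are one of the two outcomes for which the control group exists, and the results go to the regulator.

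**Working it through.** **Planned sizes.** The only event figure in the documents is for malignancy (Protocol section 3): 104 events in 4000 patients at 1.16 per 100 patient-years with about 50% drop-out at 3 years. Linear loss gives a mean of 3 × (1 + 0.5)/2 = 2.25 years, and 4000 × 2.25 × 0.0116 = 104.4, so 104 is reproduced. The Appendix table follows from 1/n1 + 1/n0 = 1/4000 + 1/2000 = 0.00075. For 2400 controls, 0.00075 − 1/2400 = 1/3000. The planned range is therefore 4000:2000 to 3000:2400. Protocol 6.3 says the contract ratio "to be specified in the contract will be in principle 2 to 1" and lets sites go to 1:1.

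**Incidence ratio.** With b = 0 the estimate divides by zero. With a = 0 its logarithm does not exist. Either way 1/a + 1/b is undefined.

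**Rate difference with b = 0.** The limits reduce to (a ± 1.96√a)/PT1. The lower limit is positive when a > 1.96² = 3.84, that is from a = 4, and PT0 has dropped out. At 4000 patient-years, per 100 patient-years:
- 3 versus 0: (3 ± 3.39)/40 = −0.010 to 0.160
- 4 versus 0: (4 ± 3.92)/40 = 0.002 to 0.198

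The planned difference in proportions has the same threshold of 4.

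**Is 4 versus 0 strong evidence at 2:1?** Given 4 events in all, each falls in the Xeljanz group with probability 2/3 under equal rates.
- One-sided exact probability: (2/3)⁴ = 0.198.
- Score statistic: (4 − 2.667)/√(4 × 2/3 × 1/3) = 1.41.
- Exact lower limit for the ratio: 0.025^(1/4) = 0.398, and 0.398/0.602 × 2000/4000 = 0.33.

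The SAP's own single-group formula agrees. Zero events in 2000 patient-years has an upper limit of 100 × (5.991/2)/2000 = 0.150 per 100 patient-years, above the observed Xeljanz rate of 100 × 4/4000 = 0.100.

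**Frequency of the error.** The documents give no rates for these infections, so expected control events of 1 to 5 are an assumption. The results depend only on the expected counts and the person-time ratio. Two independent Poisson counts with equal true rates were enumerated in full. The first four result columns give the chance that the interval wrongly shows Xeljanz worse (nominal 2.5%).

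| Expected control events | SAP difference, 4000:2000 | SAP difference, 3000:2400 | Score, 4000:2000 | Exact, 4000:2000 | No ratio interval, 4000:2000 |
|---|---|---|---|---|---|
| 1 | 5.3% | 1.4% | 0.0% | 0.0% | 45% |
| 1.5 | 7.9% | 2.8% | 0.3% | 0.0% | 26% |
| 2 | 7.9% | 3.7% | 0.7% | 0.1% | 15% |
| 3 | 5.7% | 4.0% | 1.6% | 0.5% | 5% |
| 5 | 4.7% | 3.4% | 2.0% | 1.1% | 0.7% |

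Check at 2 expected control events: P(b = 0) × P(a ≥ 4) = 0.1353 × 0.5665 = 7.7%, so nearly all of the 7.9% comes from zero-control splits. At 1:1 the chance is below 2.5% at all five values. With 0.4 expected control events at 2:1 it is only 0.6%, but 82% of surveys then have no ratio interval.

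**Larger counts.** At 40 and 20 expected events (2:1) the SAP interval errs in 5.2% of surveys over both sides. At 120 and 60 it errs in 5.1%.

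**The case against.** The strongest reply is about scope. A reader might infer that the 4-versus-0 artefact affects tuberculosis and opportunistic infection as well. It does not, because the SAP names only the incidence ratio for those. Among the rare infections only serious herpes zoster receives the rate difference. A reader might also infer that 8.1.6 contains just these two intervals, or that 4 versus 0 is misleading at any exposure. Neither holds. At 1:1 person-time a score test of 4 versus 0 gives p = 0.046.

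The person-time ratio may also be below the patient ratio. The primary serious-infection analysis counts treatment time plus 28 days up to 1 year, and control patients who switch to another non-Xeljanz drug stay under surveillance. The documents do not say how far this moves the ratio, so 2:1 is a planning figure.

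The SAP says: "Since this survey is not a confirmatory study, statistical tests will be exploratory". It specifies Fisher's exact test if a binary test is done, and exact single-group intervals would appear beside the comparison. A ratio reported as not estimable misleads nobody.

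The narrowing of scope stands in full. The rest stands in part. Exploratory status does not excuse an interval with up to three times its nominal one-sided error. Section 8.2.3.1.2 asks for intervals, not tests, on these events. And a missing ratio interval still needs a stated rule.

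The remedy has its own asymmetry. At 2:1 the score interval shows Xeljanz falsely better in 4.2%, 3.7%, 3.3% and 3.0% of surveys at 1, 1.5, 2 and 3 expected control events. It already excludes zero at 0 versus 2: (0 − 1.333)/√(2 × 2/3 × 1/3) = −2.0. False reassurance matters in a safety survey, and the fix allows for this.

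**Conclusion.** The point holds in a limited form. That the ratio interval fails when either group has no event, and that the rate difference excludes zero from 4 versus 0, follow from the printed formulas without any assumption. The size of the false-excess error rests on assumed event counts and on the person-time ratio: 4.7% to 7.9% at the five tabulated values for 4000:2000, at most 4.0% for 3000:2400, and no inflation at 1:1, against a nominal 2.5%.

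It would be wrong to conclude that the main comparisons are unsound. With about 104 malignancies planned for the Xeljanz group, and serious infections overall expected to be far more numerous than any single rare type, the large-sample formulas perform close to nominal. The weakness concerns how rare infections are reported.

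**What to change.** Add a small-count rule to SAP 8.1.6. When either group has no event or few (for example fewer than 10):
- use the exact conditional (binomial) interval for the incidence ratio, which gives a one-sided interval when one count is zero;
- use a score (Miettinen-Nurminen) interval for differences in rates and proportions;
- let the exact ratio interval decide whether an excess or a deficit is reported, because of the score interval's error in the other direction at 2:1.

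The threshold of 10 is a convention and should be written into the SAP as a fixed number. The other formulas can stay for larger counts. The exception is the printed standard error for the ratio of proportions, √(1/(a/N1) + 1/(b/N0)). It differs from the usual √(1/a − 1/N1 + 1/b − 1/N0) and needs its own check.

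The work is a few sentences and standard software options, with no new data. The real cost is sensitivity. Against 0 control events at 2:1, excluding the null would take 8 Xeljanz events by the score method ((8 − 5.333)/1.333 = 2.0) or 10 by the exact method ((2/3)¹⁰ = 0.017, while (2/3)⁹ = 0.026), instead of 4 now. The SAP should say so, so that a wide interval is not read as evidence of no difference.

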#### [Rationale for sample size]

The incidence of malignant tumor associated with Xeljanz in a domestic long-term administration study (Study No. A3921041) was 1.16 (/100 person-year). The drop-out rate in clinical studies was 31% among subjects who transferred from the domestic Phase II study (Study No. A3921039) to the domestic long-term administration study (Study No. A3921041) (treatment period: approximately 3 years), and 14% among subjects who transferred from another domestic Phase II study (Study No. A3921040) (treatment period: approximately 1.4 years); based on which, the drop-out rate at the completion of 3-year observation in daily medical practice is estimated to be approximately 50%.

If 4000 patients were to be enrolled in the Xeljanz group, the target events should be confirmable in 104 patients based on the incidence of malignant tumor in Japanese subjects, which was 1.16 (/100 person-year).

Next, assuming that 4000 patients would be enrolled in the Xeljanz group and the incidence of malignant tumor in the control group would be equivalent to the Xeljanz group, at least 2000 subjects would need to be enrolled in the control group in order to enable a statistically appropriate inter-group comparison; thus, a sample size of 2000 subjects was selected for control.

Depending on the progress of registration, if the registered number of patients in either group significantly exceeds the above number earlier than the other group, a sample size with 3-year observation period can be changed to the combination of a sample size for whom the degree of statistical accuracy is maintainable if it is compared with 4000

patients in the Xeljanz group and 2000 patients in the control group (see the Appended Table). Also, the registration period for patients in the inter-group comparison needs to be the same.

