			
6.3. Covariates
 

Added candidate covariates related to the development of malignant tumors and serious infections and created a table of the candidate covariates.

 
7. Handling of Missing Data
 

Added a handling method of missing data about candidate covariates related to the development of malignant tumors and serious infections.

 
8.1.6. Group Comparison of Incidence Rate and Incidence Proportion of Specified Events
 

Changed definition of variance in “Difference in pooled incidence proportion between the treatment groups and the 95% confidence interval”.

Specified a calculation method in “Propensity scores”.

 
8.2.2. Analysis of Patient Background and Treatment History
 

Deleted an analysis for only concomitant drugs initiated by 6 months after the start of Xeljanz in “Concomitant drugs”.

Deleted an analysis for only non-drug therapies initiated by 6 months after the start of Xeljanz in “Non-drug therapies”.

 
8.2.3.1. Analysis of malignant tumors
 

Specified a calculation method in “Adjusted hazard ratio for the development of malignant tumors”.

 
8.2.3.2. Analysis of serious infections
 

Specified a calculation method in “Adjusted hazard ratio for the development of serious infections”.

 
8.2.3.4. Safety analysis in the Xeljanz group
 

Deleted some analyses in “Subgroup analysis”.

Deleted some analyses in “Key survey items”.

 
8.2.4. Efficacy Analysis
 

Deleted percent changes.

 
8.2.4.3. Subgroup analysis
 

Changed definition of efficacy to SDAI remission after 6 months of administration

 
10. References
 

Added some references.

 
11.1.2. Patient Background
 

Added some items and categories.

 
11.1.3. Patient Background Considered for Safety
 

Added some items and categories.

 
11.1.4. Patient Background Considered for Efficacy
 

Added some items and categories.

 
Refined typos were corrected, and presentation and wording.

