**Difference in pooled incidence rates [patient/100 patient – years]**

$$= 100 \times \left\{ \frac{\sum \left( \frac{a_i PT_{0i} - b_i PT_{1i}}{T_i} \right)}{\sum \left( \frac{PT_{1i} PT_{0i}}{T_i} \right)} \right\}$$

95% confidence interval for difference in pooled incidence rates [patient/100 patient – years]

$$= 100 \times \left\{ \frac{\sum \left( \frac{a_i PT_{0i} - b_i PT_{1i}}{T_i} \right)}{\sum \left( \frac{PT_{1i} PT_{0i}}{T_i} \right)} \pm 97.5 \text{ percentile for standard normal distribution} \right. \\ \left. \times \sqrt{\frac{\sum \left( \frac{PT_{1i} PT_{0i}}{T_i} \right)^2 \left( \frac{a_i}{PT_{1i}^2} + \frac{b_i}{PT_{0i}^2} \right)}{\left( \sum \frac{PT_{1i} PT_{0i}}{T_i} \right)^2}} \right\}$$

- Ratio of pooled incidence proportions between treatment groups and its 95% confidence interval

$$\text{Ratio of pooled incidence proportions} = \frac{\sum \left( \frac{a_i N_{0i}}{S_i} \right)}{\sum \left( \frac{b_i N_{1i}}{S_i} \right)}$$

95% confidence interval for ratio of pooled incidence proportions

$$= \exp \left\{ \ln \left[ \frac{\sum \left( \frac{a_i N_{0i}}{S_i} \right)}{\sum \left( \frac{b_i N_{1i}}{S_i} \right)} \right] \pm 97.5 \text{ percentile for standard normal distribution} \right. \\ \left. \times \sqrt{\frac{\sum \left( \frac{M_{1i} N_{1i} N_{0i}}{S_i^2} - \frac{a_i b_i}{S_i} \right)}{\left( \sum \frac{a_i N_{0i}}{S_i} \right) \left( \sum \frac{b_i N_{1i}}{S_i} \right)}} \right\}$$

Xeljanz group

$a_i$ : Number of patients with the event in Stratum i [patient]

$N_{1i}$ : Number of patients in Stratum i [patient]

Control group

$b_i$ : Number of patients with the event in Stratum i [patient]

$N_{0i}$ : Number of patients in Stratum  $i$  [patient],

$$M_{1i} = a_i + b_i$$

$$S_i = N_{1i} + N_i$$

- Difference in pooled incidence proportion between the treatment groups and the 95% confidence interval

$$\text{Difference in pooled incidence proportion [%]} = 100 \times \frac{\sum \left( \frac{a_i N_{0i} - b_i N_{1i}}{S_i} \right)}{\sum \left( \frac{N_{1i} N_{0i}}{S_i} \right)}$$

95% confidence interval for the difference in pooled incidence proportion [%]

$$= 100$$

$$\times \left[ \frac{\sum \left( \frac{a_i N_{0i} - b_i N_{1i}}{S_i} \right)}{\sum \left( \frac{N_{1i} N_{0i}}{S_i} \right)} \pm 97.5 \text{ percentile for standard normal distribution} \right]$$

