In addition, the ratio of incidence proportion and the 95% confidence interval and the difference in incidence proportion and the 95% confidence interval will be calculated.

For covariates concerning malignant tumors ([Section 6.3](#)), the incidence proportion by single factor will be calculated, and the ratio of the pooled incidence proportion and the 95% confidence interval and the difference in the pooled incidence proportion and the 95% confidence interval will be calculated. Age will be handled as categorical data.

- **Analysis of time to malignant tumor**

Time to malignant tumor in each group will be summarized in accordance with [Section 8.1.4](#). As for the censoring period in patients without malignant tumors, [Table 5](#) will be followed. In addition, a graph showing the transition of the incidence rate estimated using the calculated parameters by applying the Weibull distribution together with the Kaplan-Meier plot, and a graph of the transition of the hazard function are created.

- **Adjusted hazard ratio for the development of malignant tumors**

As for time to malignant tumor, the adjusted hazard ratio of the Xeljanz group to the control group for the development of malignant tumors and the 95% confidence interval will be calculated in accordance with [Section 8.1.5](#). Covariates used for adjustment are shown in [Section 6.3](#).

As for the development of malignant tumors in the Xeljanz group compared to the control group, the propensity score-weighted (inverse probability of treatment weighting, IPTW) hazard ratio and the 95% confidence interval will be calculated. The weight is obtained

from  $Z_i + \frac{\theta_i(1-Z_i)}{1-\theta_i}$  ( $\theta_i$ : the estimated propensity score,  $Z_i$ : 1 (if xeljanz group) or 0 (if control group)). The other propensity score-weighted hazard ratio and the 95% confidence interval also will be calculated from setting an upper limit on the weight, because it is possible that some weights are too high if  $\theta_i$  is nearly equal 1. The upper limit is determined depending on a situation of the estimation accuracy.

In addition to the propensity score-weighted, further adjustment using a model with covariates of large effect will be conducted. The covariates which show large change in adjusted hazard ratio from the non-adjusted hazard ratio in the univariate model, will be included in this model in order to control the number of covariates in the model.

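### SAP 8.1.6: the confidence interval for the ratio of incidence proportions uses a standard error that ignores sample size, so it always includes 1

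*SAP*

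**What the plan says.** SAP 8.1.6 lists the quantities for comparing the two groups. With a events among N1 Xeljanz patients and b events among N0 control patients, the relevant formulas are:

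- **Ratio of proportions.** Under "95% confidence interval for ratio of incidence proportions" the interval is exp[ln(ratio) ± z × SE], with SE = sqrt[1/(a/N1) + 1/(b/N0)].
- **Pooled (stratified) ratio of proportions.** Under "95% confidence interval for ratio of pooled incidence proportions" the variance is Σ(M1i·N1i·N0i/Si² − ai·bi/Si), divided by the product of Σ(ai·N0i/Si) and Σ(bi·N1i/Si).
- **Pooled difference in proportions.** Under "95% confidence interval for the difference in pooled incidence proportion" the half-width is z × sqrt(difference × ΣUi + ΣVi).

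The ratio interval is called for in SAP 8.2.3.1.1 (malignant tumors), where "the ratio of incidence proportion and the 95% confidence interval and the difference in incidence proportion and the 95% confidence interval will be calculated". The same request stands in 8.2.3.1.2 (serious infections, also with and without serious herpes zoster) and 8.2.3.1.3 (deaths). For single covariates in 8.2.3.1.1 and 8.2.3.1.2, "the difference in the pooled incidence proportion and the 95% confidence interval will be calculated".

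**The concern.** The standard error of a log ratio of two proportions must fall as events and patients accumulate. The expression in 8.1.6 depends only on the proportions a/N1 and b/N0, so a survey of 400 patients and one of 40,000 with the same proportions would get the same interval.

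The comparison of malignant tumors and serious infections with the control group is a stated objective (Protocol section 1, SAP 2.2). If the formula were programmed as written, the ratio of proportions for these events and for deaths could never show a difference between groups, however large.

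**Working it through.** **Inputs.** SAP section 4: "A 2-sided confidence interval will be used for interval estimation, and the confidence coefficient will be 95" per cent, so z = 1.96. Protocol section 3, rationale for sample size: "If 4000 patients were to be enrolled in the Xeljanz group, the target events should be confirmable in 104 patients". The same rationale assumes equal incidence in a control group of 2000, which gives 104 × 2000/4000 = 52 control events. The figure of 52 is derived; the plan does not state it.

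**The plan's figure of 104.** With 50% drop-out by 3 years spread evenly, mean follow-up is 3 × (1 + 0.5)/2 = 2.25 years. Then 4000 × 2.25 × 0.0116 = 104.4, which agrees with 104.

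**Ratio as written.** SE = sqrt(4000/104 + 2000/52) = sqrt(38.46 + 38.46) = 8.77. The interval is exp(±1.96 × 8.77), or 3.4 × 10⁻⁸ to 2.9 × 10⁷.

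**Ratio from the SAP's own pooled formula, one stratum.** With S = N1 + N0, the numerator is (a+b)·N1·N0/S² − ab/S and the denominator is ab·N1·N0/S². The quotient is (a+b)/(ab) − S/(N1·N0) = 1/a + 1/b − 1/N1 − 1/N0. Here that is 0.009615 + 0.019231 − 0.00025 − 0.0005 = 0.028096, so SE = 0.168 and the interval is 0.72 to 1.39. The SE as written is 8.77/0.1676 = 52 times larger on the log scale.

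**Other counts.** The rows after the first are assumed counts, to show the range; the last uses the Protocol Appendix combination of 3000 and 2400 at 2.6%.

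| Xeljanz | Control | Ratio | SE as written | 95% CI as written | SE, pooled formula | 95% CI |
|---|---|---|---|---|---|---|
| 104/4000 | 52/2000 | 1.00 | 8.77 | 3.4 × 10⁻⁸ to 2.9 × 10⁷ | 0.168 | 0.72 to 1.39 |
| 208/4000 | 52/2000 | 2.00 | 7.60 | 6.8 × 10⁻⁷ to 5.8 × 10⁶ | 0.153 | 1.48 to 2.70 |
| 104/4000 | 35/2000 | 1.49 | 9.78 | 7.1 × 10⁻⁹ to 3.1 × 10⁸ | 0.193 | 1.02 to 2.17 |
| 78/3000 | 62/2400 | 1.01 | 8.78 | 3.4 × 10⁻⁸ to 3.0 × 10⁷ | 0.168 | 0.72 to 1.40 |

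**Why the interval always includes 1.** It excludes 1 only if |ln(p1/p0)| / sqrt(1/p1 + 1/p0) exceeds 1.96. For a fixed ratio r this quotient is largest when the larger proportion is 1, where it equals ln r / sqrt(1 + r). That peaks at r = 9.19 with the value 2.218/3.192 = 0.695. So no data with events in both groups can exclude 1, whatever counts are assumed.

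**Pooled difference (secondary).** With one stratum at 104/4000 and 52/2000 the difference is 0, so only V matters: V = (104 × 1948 + 52 × 3896)/(2 × 6000) = 33.77, with square root 5.811.

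- As it appears in the text, the half-width is 1.96 × 5.811 = 11.39, or 1139 percentage points. A difference of proportions cannot exceed 100.
- Divided by Σ(N1i·N0i/Si) = 4000 × 2000/6000 = 1333.3, the SE is 0.004358 and the half-width 0.854 points.
- The SAP's unpooled formula, sqrt[a(N1−a)/N1³ + b(N0−b)/N0³], also gives 0.004358.
- At 208/4000 against 52/2000 the half-widths are 1306 without the divisor and 0.980 with it. The unpooled formula again gives 0.980.

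**The case against.** The best case against acting is that the practical harm is small and conditional. The documents do not show any program built from these formulas, and standard software would give the usual interval. An interval from 10⁻⁸ to 10⁷ would be noticed in the first table. The ratio of proportions is also not the main instrument: Protocol 8.3 item 2 relies on exposure-based rates, the adjusted hazard ratio and a matched control subset, and SAP section 4 calls the tests exploratory. All of this stands and limits the weight of the point. It does not make the formula right, and the SAP still specifies this interval for three outcomes.

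A second objection is that the text may be damaged. For the pooled difference this has force. The formula is broken in two, its bracket closes before the square root begins, and a single outer denominator could easily be lost in converting the page to text. The U and V terms are correct, and the neighbouring pooled rate difference carries its squared denominator. For the ratio the objection is weak: that expression is complete, unbroken, and repeats the a/N1 and b/N0 of its own point estimate.

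A reader might also treat Si, which appears as N1i + Ni, as a further error. One lost subscript character explains it, and N0i is defined just above, so I do not count it.

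**Conclusion.** The standard error for the ratio of incidence proportions in SAP 8.1.6 is wrong as written. Confidence is high, because the SAP's own pooled formula contradicts it and the result that the interval always includes 1 needs no assumed counts. The factor of 52 does rest on the planning figures: 104 events, and the derived 52.

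The pooled difference is a secondary point of medium confidence. As it stands in the text it lacks the divisor Σ(N1i·N0i/Si), but whether the SAP page lacks it is not established.

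Three stronger readings are tempting and are not supported:

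- **That reported results are wrong.** The documents contain neither program code nor results.
- **That the safety comparison as a whole is compromised.** Point estimates, rate ratios and differences (crude and pooled), the pooled ratio of proportions, the unpooled difference in proportions and all hazard ratios are unaffected.
- **That outputs from before version 7.0 need an audit.** The change log entry for the pooled difference ("Changed definition of variance in") records a revision, but the earlier formula is not shown, so nothing can be said about it.

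**What to change.** 1. Replace the standard error of the log ratio of incidence proportions in SAP 8.1.6 with sqrt(1/a − 1/N1 + 1/b − 1/N0), by erratum.
2. Check that the programs and issued tables for the ratio of proportions use that form, for malignant tumors, serious infections (including the two herpes zoster splits) and deaths.
3. Compare the pooled-difference formula with the original SAP page. If the divisor is absent there, divide the square root by Σ(N1i·N0i/Si) in the same erratum, and check the single-factor tables for malignant tumors and serious infections.

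The cost is low: a text correction and a short program check. It would be a further documented change after database release, as version 10.0 already was. If standard software was used, the results may already be right and only the text changes.
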